2. ADDITIONAL RELEVANT INFORMATION

Not applicable.

3. CONCLUSION

In conclusion, Pfizer considers that the results of the nonclinical toxicity and safety pharmacology studies together with the data from the clinical program confirms that treatment with sildenafil in patients with PAH of various etiologies and severities is associated with improvements in exercise ability and favorable effects on hemodynamics and other measures of efficacy such as BORG Dyspnea Score, WHO Functional Class, QoL, and use of background medication. Additionally, the potential long-term effectiveness of this agent is suggested as demonstrated in open label studies A1481142 and A1481153. Risks to subjects with PAH are minimized through appropriate pre-enrollment screening, specific exclusion criteria, and close safety monitoring throughout the study including the use of an external data safety monitoring committee. Clinical events will be adjudicated by a Clinical Endpoint Adjudication Committee.

Complete information for this compound may be found in the Summary of Data and Guidance for Investigator (Section 7) of the Investigator's Brochure.

Appendix 6: Continuity of study treatment and dose adjustment (5 mg to 20mg (TID)) in Ukraine, Russia, Czech Republic, Bosnia and Herzegovina, and Mexico.

A planned interim analysis was conducted after 50% of the required number of events (72 deaths) occurred (data cutoff 30 May 2020). The Data Monitoring Committee (DMC) subsequently convened on 01 July 2020 to review the results of the interim analysis based on the primary efficacy endpoint of time to death.

The DMC recommended and the formal notification was received by Pfizer on 07 July 2020 to stop the trial for the following reasons:

1. Primary Study Objective - noninferiority of sildenafil 80 mg (TID) vs 5 mg (TID) dose with respect to mortality - was met
2. Safety concern regarding mortality with sildenafil 5 mg (TID) dose

Following acceptance of the DMC recommendation on 08 July 2020, an Investigator's Letter was sent to all participating sites on 13 July 2020 communicating the DMC recommendation. Sites were instructed to initiate the study closeout activities by scheduling an End of Treatment Visit no later than 15 August 2020 for all subjects currently receiving study treatment. After completing the End of Treatment Visit, subjects may continue on prescription sildenafil and/or other available therapies, at the investigator's discretion.

The sites with subjects who do not have post-study PAH treatment options currently available received a second Investigator's letter, on 30 July 2020. For those subjects, sites were instructed to schedule a regular Study Visit before 15 August 2020 to ensure that all subjects receiving sildenafil 5 mg (TID) discontinue their treatment as soon as possible and continue on 20 mg (TID) (the currently approved dose). This needs to be accomplished in a blinded fashion at the scheduled visit as follows:

- Subjects must be informed about the DMC recommendation and their consent to continue in the study obtained.
- Subjects must be informed that if they agreed to continue participation in the study and are currently receiving 5 mg (TID), their dose would be automatically increased to 20 mg (TID); for subjects currently receiving either 20 mg sildenafil (TID) or 80 mg sildenafil (TID), the dose would remain unchanged. Both the investigator and the subject will remain blinded to the study treatment.
- A new blinded study drug kit will be assigned and dispensed to all subjects.

The IVRS/IWRS system will be set to close the sildenafil 5 mg (TID) treatment arm and to replace it with sildenafil 20 mg (TID). This will ensure that all subjects in the 5 mg TID arm will be increased to 20 mg TID in a blinded manner, as follows:

1. Subjects on 5 mg TID will be increased to 20 mg TID and will continue in the study on 20 mg TID until the End of Treatment Visit.
2. For subjects on 20 mg TID or 80 mg TID, the dose will remain unchanged until the End of Treatment Visit.

To ensure continuity of study treatment with sildenafil, subjects are allowed to stay in the study until they can be enrolled into a program that will provide access to prescription sildenafil at the time of the End of Treatment Visit.

After completing the End of Treatment Visit, a 28-day follow-up visit will be scheduled at which time the End of Study CRF page will be completed. This will conclude the subject's participation in the trial.

1. AMENDMENTS FROM PREVIOUS VERSION(S)

Version	Date	Author(s)	Summary of Changes/Comments
2	March 24, 2021	PPD	
As of protocol amendment 1, dated 18 Nov 2014 the following changes have been incorporated:
 
 Added definition of on-treatment deaths to Section 8.1. 
As of Blind Data Review (BDR1), dated 19 Aug 2019 the following changes have been incorporated:
 
 Updated Section 4.1 to include secondary hypotheses/treatment comparisons for 80 mg vs. 20 mg, and 20 mg vs. 5 mg. Clarified text for Safety population (Section 5.3). For this study Safety population is the same as ITT population. Added rules for randomization stratification misallocations in Section 5.5. Updated Section 6.1 categories labels for Change from Baseline in 6MWD 6 Month Walking Distance). Updated Section 6.2 to include reference to protocol section referring to non-efficacy endpoints screening definitions. Updated Section 8.1 to include secondary treatment comparisons for 80 mg vs. 20 mg, and 20 mg vs. 5 mg as secondary analysis of primary efficacy endpoint (time-to-death). Updated Section 8.2 to include 6MWD change from baseline at Month 6 as a secondary endpoint. Added 6MWD change from baseline at Month 6 as a secondary analysis to Table of summary of efficacy analyses in Section 8.3. Added a super script “2” to Table 3 to refer to the Borg Score analysis for change from baseline, by randomization stratification factors (Subgroup column).

			
 • Added two new references to Section 10. • Added algorithm for calculation of PAH at treatment stratification in Appendix 11.1. • All SAS & StatExact Codes are presented in Appendix Sections 11.2.1-11.2.6. • Updated Appendix 11.2.1 and 11.2.4 on SAS code for the Cox Proportional Model and MMRM analysis models, respectively. • Added visit window for secondary and tertiary endpoints to Appendix 11.3. 
As of protocol amendment 2, dated 28 August 2020 the following changes has been incorporated:
 
 • Added to Section 8.2 a sensitivity analyses for time to first adjudicated clinical worsening events. • Added a new Section 9 for DMC review of unblinded interim analysis and its recommendation. This recommendation led to an update regarding study conduct and currently includes a new safety sensitivity analysis for death and SAEs. • Added sensitivity safety analysis for subjects who were switch from 5 mg to 20 mg treatment (Section 9.1).
--	--	--	--

2. INTRODUCTION

This document describes the planned data summaries and statistical analyses for Protocol A1481324, entitled “A Multi-national, Multicenter Study to Assess the Effects of Oral Sildenafil on Mortality in Adults with Pulmonary Arterial Hypertension (PAH)”. It is meant to supplement the study protocol which should be referred to for details regarding the objectives and design of the study. Any deviation to this analysis plan will be described in the Clinical Study Report.

Note: in this document any text taken directly from the protocol is *italicised*.

2.1. Study Design

This is a randomized, double-blind, parallel-group study in adult subjects with PAH that is designed to assess mortality during long-term treatment with sildenafil at three doses. Four hundred and twenty-nine (429) subjects will be enrolled to allow approximately 143 subjects to be randomly assigned to each arm. Approximately 80-120 sites with experience conducting PAH trials will participate in the study. The study is expected to complete enrollment in approximately 4.3 years with total duration of about 7.7 years to reach required number of events (143 deaths).

Subjects will be randomly assigned on a 1:1:1 basis to either blinded sildenafil 5 mg (TID), 20 mg (TID) or 80 mg (TID) at the Baseline visit (Day 1) after successfully fulfilling all inclusion and exclusion criteria. Randomization will be stratified according to PAH treatment at entry (PAH-treatment naïve vs. on PAH-treatment) and etiology of PAH (idiopathic vs. secondary to CTD/surgical repair). Blinded sildenafil treatment is to continue for the duration of the subject’s participation in the study. Subjects who discontinue from the trial will continue to be followed for the primary endpoint.

2.2. Study Objectives

Primary objective: Test for the non-inferiority of sildenafil 80 mg vs. 5 mg for mortality; mortality rate with the 80 mg dose is no worse than double the mortality rate for the 5 mg dose.

3. INTERIM ANALYSES, FINAL ANALYSES AND UNBLINDING

An independent Data Monitoring Committee (DMC) will be engaged to review efficacy endpoints including mortality rate, clinical worsening and other safety data, safeguard the interest of study subjects and provide recommendations on continuing the conduct of the study.

The DMC will be responsible for ongoing monitoring of the safety of subjects in the study according to the DMC Charter. The DMC is to meet at least twice per year to review aggregate safety data throughout the study. In addition, the DMC will meet after each interim analysis with formal hypotheses testing; the recommendations made by the DMC to alter the conduct of the study will be forwarded to Pfizer for final decision.

Interim analyses with statistical analyses on hypotheses testing will be performed for primary comparison of 80 mg vs 5 mg when about 50% and 75% of mortality events have occurred.

O'Brien-Fleming approach will be used for decision making, ie, reject H_0 with 1-sided p-value <0.0015 , and <0.0092 for the interim analyses with 50% and 75% of the mortality events, respectively, or reject H_1 with 1-sided p-value >0.3701 and >0.0982 for the interim analyses with 50% and 75% of the mortality events, respectively. The final p-value for rejecting H_0 will be <0.022 (1-sided). The actual stopping boundaries will depend on the exact timing of each interim analysis.

Treatment unblinding to study team members, investigators and subjects and final analyses will be done after the database lock.

4. HYPOTHESES AND DECISION RULES

4.1. Statistical Hypotheses

The primary objective for the study is to test for the non-inferiority of sildenafil 80 mg TID vs. 5 mg TID for mortality; mortality rate with the 80 mg TID is no worse than double the mortality rate for the 5 mg TID.

The hypotheses for the primary endpoint of mortality are:

- H_0 : hazard ratio (80 mg TID /5 mg TID) ≥ 2 ;
- H_1 : hazard ratio (80 mg TID /5 mg TID) < 2 .

The hypotheses will be tested at an overall level of 2.5% (1-sided).

Additional treatment comparisons for 80 mg vs 20 mg, and 20 mg vs. 5 mg will be performed where these will be considered secondary comparisons. There will be no p-value adjustment for multiplicity.

4.2. Statistical Decision Rules

If the 1-sided upper confidence limit of the hazard ratio (80 mg TID/5 mg TID) is less than 2, then the null hypothesis that the mortality rate in the 80 mg TID is worse than double the rate in 5 mg TID will be rejected. In case that the hazard ratio is statistically significantly less than 1, then superiority of 80 mg TID over 5 mg TID will be claimed.

5. ANALYSIS SETS

5.1. Full Analysis Set

The intent-to-treat population (ITT) will consist of all randomized patients treated with study treatment. The primary efficacy analysis will be conducted using ITT population.

5.2. 'Per Protocol' Analysis Set

The Per-protocol population (PP) will consist of randomized subjects who receive at least 1 dose of study treatment and contribute at least 1 post-baseline visit. The time to event endpoint for this PP will consist of all events that occur while the subjects are on study treatment without major protocol deviations/violations through 35 days after the last dose of the study treatment, since randomization. This collection period (from randomization to

35 days after the last dose of the study treatment) will also be applied to other efficacy endpoints with PP analyses.

The efficacy analyses of primary and secondary endpoints will be conducted using the per-protocol (PP) population as sensitivity analyses.

5.3. Safety Analysis Set

The safety analysis set will include all randomized subjects treated with study treatment (same as ITT population).

5.4. Treatment Misallocations

If a subject is:

- Randomized but not treated, then they will be reported under their randomized treatment group but will not be included in the efficacy analyses and safety analyses as actual treatment is missing.
- Treated but not randomized, then by definition they will be excluded from the efficacy analyses since randomized treatment is missing but will be reported under the treatment, they actually received for all safety analyses.
- Randomized but took incorrect treatment, then they will be reported under their randomized treatment group for all efficacy analyses but will be reported under the treatment they actually received for all safety analyses.

5.5. Randomization Stratification Misallocations

- Randomized as PAH Treatment Naïve but should have been randomized as On PAH Treatment.
- Randomized as On PAH Treatment but should have been randomized as PAH Treatment Naïve.

Classification of a patient into these stratum will be done programmatically and is presented on [Appendix 1](#).

Subjects will be put in the stratum that reflects clinical reality and will be analyzed under the correct determined stratum, ie, stratum determined by clinical data that they should have been randomized. A data listing will be provided for subjects with randomization stratification error.

5.6. Protocol Deviations

Significant protocol deviations may include, but not limited to:

- Failure to meet significant inclusion/exclusion criteria.

- No evidence of adequate compliance to study medication (See Protocol Section 5.3.4 for definition of compliance).
- Receiving excluded concomitant medication.

Protocol deviations (including list of excluded concomitant medications) which lead to exclusion of subjects from PP analyses will be specified before database lock.

BORG will be measured at Screening, Day 1 and every 6 months during the study, and at the end of study treatment. Measurement taken on Day 1 will be considered as Baseline value. If Day 1 value is missing and the one taken at Screening is non-missing, then the value taken at Screening will be considered as the baseline value. Change from baseline at each study visit will be calculated as (Result at Post Baseline Study Visit) – (Baseline Value). The visit windows defined for 6MWD above will also apply to BORG score (see [Appendix 3](#)).

C. WHO pulmonary hypertension functional class (tertiary endpoint)

WHO pulmonary hypertension functional class will be measured at Screening, Month 3, 6, 9, 12 and every 6 months subsequently during the study, and at the end of study treatment. Measurement taken at Screening will be considered as Baseline value. Change from baseline at each study visit will be calculated as (Result at Post Baseline Study Visit) – (Baseline Value). Visit windows for this tertiary endpoint are defined in [Appendix 3](#).

6.2. Safety Endpoints

A. Treatment-emergent Adverse Events (AE)

A treatment-emergent AE is an AE with an onset after initiation of study treatment, or an AE present at initiation of study treatment that subsequently worsens (ie, increases in severity or relationship to study treatment).

A 3-tier approach will be used to summarize treatment-emergent AEs. Under this approach, AEs are classified into 1 of 3 tiers. Different analyses will be performed for different tiers (See [Section 8.4](#)).

Tier-1 events: These are pre-specified events of clinical importance and are maintained in a list in the product's Safety Review Plan.

Tier-2 events: These are events that are not tier-1 but are "common". A MedDRA PT is defined as a tier-2 event if there are at least 5% in any treatment group.

Tier-3 events: These are events that are neither tier-1 nor tier-2 events.

B. Other Safety Endpoints

- Serious AE (SAE);
- Death;
- Concomitant medication;
- Subject discontinuation;
- Vital signs;
- Laboratory results;
- Physical examination;
- Duration of treatment.

For non-efficacy endpoint, study follows protocol screening definition (see Section 6.1 in protocol).

6.3. Covariates

The analyses of the primary and secondary endpoints will be performed using the following two randomization stratification factors as covariates:

- PAH treatment at entry (PAH-treatment naïve vs. on PAH-treatment);
- Etiology of PAH (idiopathic vs. secondary to CTD/surgical repair).

The analyses of 6MWD will also include baseline results as a covariate.

7. HANDLING OF MISSING VALUES

Missing data will not be imputed. For 6MWD at Month 6 and 12, mixed model for repeated measure method (MMRM) will be used for statistical analyses for treatment comparisons. For MMRM, all available data in Month 6 and 12 will be included in the analyses and any missing data are assumed missing at random. Details of the analyses are described in [Section 8](#).

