2.2. Endpoints

This study will use an independent endpoint adjudication committee to determine whether certain investigator-reported events meet the definition of disease-related efficacy endpoints, using pre-defined endpoint criteria.

For those serious adverse events (SAEs) that are handled as disease related efficacy endpoints (which may include death), a data monitoring committee (DMC) will conduct unblinded reviews on a regular basis throughout the trial (see Data Monitoring Committee Section).

Any SAE that is adjudicated by the endpoint adjudication committee NOT to meet endpoint criteria is reported back to the investigator site of incidence; the investigator at the study site must evaluate and report that SAE to Pfizer, in accordance with the time frames described in the Serious Adverse Event Reporting Requirements section of this protocol. The investigator's SAE awareness date in this instance is identified as the date on which the investigator site of incidence receives the nonendpoint SAE back from the endpoint adjudication committee. Handling these SAEs in this manner will allow Pfizer to meet its sponsor reporting obligations to regulatory authorities upon receipt of such SAEs.

However, when the investigator has judged the SAE to have a causal relationship with the investigational product, the investigator must additionally report the event to the sponsor as described in the Serious Adverse Event Reporting Requirements section, even if that event is a component of the endpoint.

Any events that remain unadjudicated at the annual safety report cutoff date will not be included in the safety tables of the report.

Primary Efficacy Endpoint:

- Time to death (Mortality).

Secondary Efficacy Endpoints:

- Time to first event (Clinical Worsening); and
- 6MWD at Months 6 and 12.

Clinical worsening⁸ for the purpose of this study is defined as:

- All-cause mortality;
- Hospital stay for worsening PAH (including but not limited to right heart failure [RHF], initiation of prostanoids, lung transplantation, or septostomy); or

- Disease progression (defined as a reduction from baseline in the 6MWD test by at least 15% and worsening functional class from baseline, both confirmed by a 2nd test/evaluation within 2 weeks (cannot be performed on same day). Patients with functional class IV at baseline only need to meet the 6MWD criteria as they cannot have deterioration in functional class. The date of the event will be the first date of the two 6MWTs.

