9.1. Sample Size Determination

Total of 429 subjects will be randomly assigned into sildenafil 5 mg TID, 20 mg TID and 80 mg TID treatment group with 143 subjects in each treatment group.

This non-inferiority study is powered at 90% to test the following hypotheses at overall significance level of 0.025 (1-sided):

- H_0 : hazard ratio (80 mg TID /5 mg TID) ≥ 2 ;
- H_1 : hazard ratio (80 mg TID /5 mg TID) < 2 .

The sample size of the study is calculated based on the following assumptions:

- Equal mortality rate of 15% at 2-years for each arm;
- Accrual rate of 100 subjects/year;
- Two interim analyses with O'Brien-Fleming approach possibly rejecting H_0 or H_1 ;
- Estimated 20% drop-out rate (including lost to follow-up).

With the estimated recruitment rate, the study is expected to complete enrollment in about 4.3 years with total duration of about 7.7 years to reach required number of events (deaths) of 143.

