8.2. Efficacy Analyses for Secondary and Tertiary Endpoints

There will be no p-value adjustment for secondary and tertiary data analyses.

A. Time to First Event of Clinical Worsening

Cox proportional hazard model, analyses using Kaplan-Meier method described above will be used for time to first event of clinical worsening. The analyses will be done using ITT population and PP population for overall subjects and by randomization stratification factors.

In addition, a summary table will be presented showing n(%) of subjects with first qualifying clinical worsening event by event (none, all-cause mortality, non-elective hospital stay for worsening PAH or disease progression) for each study treatment group using ITT and PP population for overall subjects and by randomization stratification factors.

Sensitivity analysis for the secondary endpoint time to first event of clinical worsening will be performed for adjudicated clinical worsening events. All the above described analysis will be conducted.

B. 6MWD

For change from baseline, descriptive summaries (n, mean, SD, 95% CI of the mean, median, and range) will be tabulated at each study visit for each treatment group using ITT and PP population for overall subjects and by randomization stratification factors.

Percent of subjects in each category of 6MWD and change will be tabulated at each study visit for each treatment group using ITT and PP population for overall subjects and by randomization stratification factors. The 95% CI of the percentage will also be tabulated (except for the category of 'missing').

For change from baseline at Month 6 and Month 12, treatment comparisons will be conducted using MMRM with covariates of baseline value, treatment and randomization stratification factors. Least square mean difference, its 95% CI and p-value will be tabulated for each treatment comparison (sildenafil 80 mg TID vs. 5 mg TID, 80 mg TID vs. 20 mg TID and 20 mg TID vs. 5 mg TID).

Analyses will be done based on ITT and PP populations for overall subjects and subgroups by randomization stratification factors.

Figures will be provided for the least square mean change from baseline and 95% CI at Month 12 for each study treatment group for ITT population and PP population for overall subjects and by randomization stratification factors.

C. BORG Score

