For change from baseline, descriptive summaries will be tabulated at each study visit for overall and by randomization stratification factors for each treatment group.

The BORG assessment will only be valid for analysis at any specific timepoint if a 6MWT has been performed on the same day. If a BORG assessment is recorded on a different day from the 6MWT then the BORG results for that timepoint will be considered missing.

A non-parametric analysis using stratified Wilcoxon (Van-Elteren) method will be used for treatment comparison at Month 12. The stratified Wilcoxon test will include randomization stratification factors. The median difference and its 95% CI calculated using the Hodges-Lehmann estimator will be presented along with the p-value for the Van-Elteren test for each treatment comparison (sildenafil 80 mg TID vs. 5 mg TID, 80 mg TID vs. 20 mg TID and 20 mg TID vs. 5 mg TID). The analyses will be done for ITT population for overall subjects.

D. WHO Pulmonary Hypertension Functional Class

The number and percentages of subjects with each WHO pulmonary hypertension functional class will be tabulated by study visit, for overall and by randomization stratification factors for each treatment group. In addition, a table will be presented by study visit showing number and percentages of subjects improving by at least 2 classes, improving by 1 class, not changing, worsening by 1 class, worsening by at least 2 classes, discontinued, died or missing. The table will be presented for overall and by randomization stratification factors for each treatment group.

The analyses will be done for ITT population for overall subjects and by randomization stratification factors.

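### The Month 6 and 12 walk-distance model treats walks missing through death as missing at random, and no planned 6MWD comparison counts death as a bad outcome, so excess deaths in one arm could be masked.

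*SAP*

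**What the plan says.** Protocol Section 2.2 makes "6MWD at Months 6 and 12" a secondary endpoint. SAP Section 7 states that "Missing data will not be imputed" and, for the repeated-measures model of those two visits, that "any missing data are assumed missing at random". SAP Section 8.2 B adds that "treatment comparisons will be conducted using MMRM with covariates of baseline value, treatment and randomization stratification factors". The sample code in SAP Appendix 2.4 also has visit and treatment-by-visit terms and an unstructured covariance.

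The summary table in SAP Section 8.3 lists this model as the only inferential 6MWD method, run on the ITT and PP sets. The other 6MWD rows are descriptive. The readable text contains no rank-based, composite or missing-not-at-random 6MWD analysis.

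Two other parts of the SAP are relevant:

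- In Section 8.2 D, the WHO functional class table gives death its own category, separate from missing.
- For BORG, Section 8.2 C specifies a rank method: "A non-parametric analysis using stratified Wilcoxon (Van-Elteren) method will be used for treatment comparison at Month 12". Code is in Appendix 2.6.

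**The concern.** The trial exists because mortality may depend on dose, and death is its primary endpoint. A missing-at-random model asks what the Month 12 walk would have been had the subject still been there, given baseline, strata and any Month 6 walk. For a subject who has died, that quantity does not exist. A subject who dies before any post-baseline walk adds nothing to the fit. One who dies between the visits is carried forward implicitly through the Month 6 value. The PP repeat uses the same model and so does not test the assumption.

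The Protocol background asks whether a dose below 20 mg TID could match it for efficacy while being safer, and the efficacy evidence it cites for 5 mg TID is walk distance. At stake is a 6MWD result that reads as no difference between doses while one arm has lost more subjects to death.

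**Working it through.** **Plan's own figures.** The documents give no sample size or power for 6MWD. The mortality inputs used below come from a calculation that reproduces. Freedman's formula with margin 2, one-sided 0.025 and 90% power gives (1.960 + 1.282)² × ((2 + 1)/(2 − 1))² = 10.507 × 9 = 94.6, so 95 deaths in the two compared arms. Across three equal arms this is 95 × 1.5 = 142.5, against the stated 143. With the 20% drop-out spread over 7.7 years, 143 deaths are reached at 7.69 years (stated: 7.7).

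**Inputs**

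- Mortality: "Equal mortality rate of 15% at 2-years for each arm" (Protocol 9.1).
- Doubled hazard: the trial's own benchmark, since the null is "hazard ratio (80 mg TID /5 mg TID) ≥ 2" (Protocol 9.1).
- Arm size: 143 (Protocol 5.1).
- SD of 6MWD change: assumed 50 to 70 m, centred near 59 m, the average of 60.950 and 57.557 m quoted for A1481243 in Protocol 1.1. That was a 12-week study on background bosentan, so the value is only a guide.

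**Deaths before each visit**, assuming a constant hazard h = −ln(0.85)/2 = 0.0813 per year

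| Hazard | Dead by Month 6 | Dead by Month 12 |
|---|---|---|
| Planned | 1 − exp(−h/2) = 4.0% | 1 − exp(−h) = 7.8% (11.2 of 143) |
| 1.5 × planned | 5.9% | 11.5% (16.4 of 143) |
| 2 × planned | 7.8% | 1 − exp(−2h) = 15.0% (21.5 of 143) |

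**What the planned model shows.** A large-sample simulation of the two-visit model assumed no dose effect on walking, SD 60 m and between-visit correlation 0.7. The log-hazard rose by 0, 0.5 or 1 per SD of worse walking. Rounded Month 12 differences, as the arm with more deaths minus the other, were:

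- hazard ratio 1: about 0 m;
- hazard ratio 1.5: 0 to +1 m;
- hazard ratio 2: 0 to +2 m.

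**What ranking death worst shows.** Let sA and sB be survival in the higher- and lower-mortality arms, with survivors walking equally. The win probability for arm A is sA(1 − sB) + ½sA·sB + ½(1 − sA)(1 − sB), which simplifies to ½ + ½(sA − sB). The equivalent normal shift is √2 × probit(win probability) × SD.

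| Visit, hazard ratio | Win probability | Shift (SD units) | Shift for SD 50 to 70 m |
|---|---|---|---|
| Month 12, 2 | ½ − ½(0.150 − 0.078) = 0.464 | −0.128 | −6.4 to −8.9 m |
| Month 12, 1.5 | ½ − ½(0.115 − 0.078) = 0.482 | −0.065 | −3.3 to −4.6 m |
| Month 6, 2 | ½ − ½(0.078 − 0.040) = 0.481 | −0.068 | −3.4 to −4.7 m |

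In the simulation at hazard ratio 2, the Month 12 win probability was 0.464 when death was unrelated to walking. It was 0.473 and 0.480 when worse walkers died sooner, so 0.464 is the clearest case, not the only one.

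**Scale.** With 85% observed, the model's standard error is SD × √(2/(143 × 0.85)) = 0.128 SD, or 7.7 m at SD 60. The Month 12 shift at hazard ratio 2 is therefore about one standard error whatever the SD. The null standard error of the win probability is √(287/(12 × 143²)) = 0.034. Hence z is about −1.05 at hazard ratio 2 (power about 18%, two-sided 0.05) and −0.54 at 1.5 (about 8%).

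**The case against.** The strongest reply is that the rank figure and the model figure answer different questions. If survivors walk equally, 0 m is the right answer for walking while alive, and −6 to −9 m measures another estimand, not bias in the model. That stands. The title to worry is only that no planned 6MWD comparison reflects death.

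A reader might go further and infer that the model would make a more lethal dose look better on exercise capacity because its sickest walkers drop out. The check does not support this: the distortion is at most about +2 m at doubled mortality, roughly a quarter of a standard error. Scoring death as 0 m gives −21 to −27 m in the same simulation, but that rests on an assumed mean baseline of 350 m that is not in the documents, so I do not rely on it.

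Other points that stand:

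- Mortality is the primary endpoint and is compared for all dose pairs, with survival tabulated by year (SAP 8.1). Clinical worsening combines death with confirmed walk decline and functional-class worsening. 6MWD p-values are unadjusted and enter no decision rule.
- The visit windows are wide (SAP Appendix 3.1: Day 2 to 274 and Day 275 to 456), and a walk is scheduled at End of Treatment. Some subjects who die will have a usable value, so 7.8% and 15.0% are upper limits for walks lost to death.
- The 6MWD definition in SAP 6.1 is incomplete in the text available to me. I cannot tell whether inability to walk is already scored.

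The reply that mortality was planned as equal is weaker. The interim stop on the primary objective, at a boundary of one-sided p < 0.0015, implies an observed 80 mg/5 mg hazard ratio below about 0.82 to 0.88. This uses 2·exp(−2.968 × 2/√d), with an assumed d = 44 to 52 of the 72 deaths in those two arms.

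**Conclusion.** The gap is real and modest. SAP Section 7 applies missing at random to walks lost through death, and nothing planned for 6MWD shows how the comparison changes when death counts as a bad outcome. The consequence is masking. At doubled hazard the model reads about 0 m where a worst-rank comparison gives a win probability of 0.464, about one standard error. At equal mortality the two agree.

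These sizes assume a constant hazard from the planned 15% two-year mortality, equal walking among survivors and an SD of 50 to 70 m.

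Because Protocol Appendix 6 reports a mortality concern for 5 mg TID, a reader might infer that the 6MWD comparison in fact favoured that arm. The documents give no hazard ratio, no deaths by Month 12 per arm and no 6MWD results, so that cannot be concluded. The primary mortality conclusion is not in question.

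**What to change.** Keep the mixed model and make four additions to SAP Sections 7, 8.2 B and 8.3:

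1. State that the model assumes values after death are missing at random, and that its means must be read with that in mind.
2. Add a pre-specified sensitivity analysis at Months 6 and 12 with death ranked worst (earlier death lower), tested by the stratified Wilcoxon (Van Elteren) method already specified for BORG.
3. Rank documented inability to walk next above death, unless the SAP 6MWD definition already scores it. State what happens to living subjects whose walk is missing for other reasons. Leaving them out would be consistent with the no-imputation rule.
4. Show the percentage dead by Months 6 and 12 per arm beside the model means.

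The cost is a few sentences of SAP text, one derived rank variable and reuse of the Appendix 2.6 code. The rank result is harder to interpret in metres and has low power by itself, so it should be labelled a robustness check. SAP Section 9 says the study team stays blinded until final database lock. The addition is pre-specified only if made before then; later, it should be labelled post hoc.
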